Human Laboratory Procedures (Specific Aim 1) Stress-Reactivity Assessment (Salivary Cortisol, HR, BP, Craving) Alcohol Demand, Alcohol Ladder	X				X
Natural Environment Procedures (Specific Aim 2) Alcohol Use and Craving (Self-Report, BrAC, ETG, PACS) Stress and Anxiety (HAM-A, PSS, BDI-II, PCL-5) Delay Discounting, Alcohol Demand	X	X	X	X	X
Natural Environment Procedures (Specific Aim 2) Alcohol Use and Craving (Self-Report, BrAC, ETG, PACS) Stress and Anxiety (HAM-A, PSS, BDI-II, PCL-5) Delay Discounting, Alcohol Demand	X	X	X	X	X

SCID - Structured Clinical Interview for DSM-5; **ASI** - Addiction Severity Index⁴⁹; **KMSK** - Kreek-McHugh-Schluger-Kellogg scale⁵⁰; **TLFB** - Timeline Followback⁵¹; **CIWAA** - Clinical Institute Withdrawal Assessment for Alcohol⁵²; **AUDIT** - Alcohol Use Identification Test⁵³; **BrAC** - Breath Alcohol Concentration; **ETG** - Ethyl Glucuronide; **PACS** - Pennsylvania Alcohol Craving Scale⁵⁴; **HR** - Heart Rate; **BP** - Blood Pressure; **HAM-A** - Hamilton Anxiety Rating Scale⁵⁵; **PSS** - Perceived Stress Scale⁵⁶; **PCL-5** - PTSD Checklist for DSM-5; **BDI-II** - Beck Depression Inventory - II.

Participants, Recruitment, and Setting. Participants (**N=20**) will consist of non-treatment and treatment-seeking individuals diagnosed with AUD (DSM-5) between 21 to 40 years old and fluent in English; past month excessive alcohol use (>7 drinks/week for women, >14 drinks/week for men, >3 drinks/occasion for women>4 drinks/occasion for men)¹⁴; baseline HAM-A or PSS Score indicative of mild to moderate anxiety (score 8 to 23) or moderate stress (score 14 to 26), respectively; and increase in alcohol craving following the

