baseline stress reactivity assessment. Individuals will be excluded for exhibiting severe scores on the HAM-A, PSS, BDI-II, or PTSD checklist (PCL-5) at the discretion of the admitting physician ([name]); physical dependence on alcohol; greater than mild substance use disorder on drugs other than alcohol, nicotine, and marijuana; contraindications for taking pioglitazone; medical conditions contraindicating pioglitazone pharmacotherapy or taking contraindicated medications; be pregnant, nursing, or planning on becoming pregnant during the course of the study; have any other illness, condition, or use of medications, which in the opinion of the PI and/or admitting physician would preclude safe and/or successful completion of the study. Recruitment strategies will include local advertising in print media, public service announcements on radio, and referrals to CNRA in the Houston metropolitan area.

Baseline Screening. Participants will receive a comprehensive medical and psychiatric evaluation including: a medical-history questionnaire, physical examination, laboratory chemistries (e.g., blood chemistry screen, complete blood count, urinalysis and urine pregnancy test), and ECG. Clinicians will conduct the **SCID**, the **ASI ASI**⁴⁹, the **KMSK**⁵⁰ assessment of lifetime substance use interview, and **TLFB**⁵¹. Alcohol dependence will be assessed using the SCID and the **CIWAA**⁵².

Alcohol-Related Measures. Assessment of alcohol use will include self-report (**TLFB**), **BrAC** (Alco-Sensor FST, Intoximeters, Inc., Saint Louis, MO). Severity of alcohol use will be assessed using the **AUDIT**⁵³. **Motivation to quit** will be assessed using the Alcohol Ladder questionnaire. **Alcohol craving** will be assessed using a 5-item questionnaire⁵⁷. ETG will be assessed using dipcards with a 300 ng/ml cutoff. ETG dipcards show good agreement with traditional immunoassays⁵⁸⁻⁶⁰.

Behavioral Economic Measures. Alcohol demand will be assessed via the **Brief Assessment of Alcohol Demand** (BAAD)⁴², a 3-item questionnaire measuring the three most common indices of alcohol demand. **Delay discounting** will be assessed for both money and alcohol using a computerized task at weekly clinic visits developed by [name] (PI)^{61,62,71,63-70}.

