Medication Compliance. One week supplies of the study medication will be dispensed with a Medication Event Monitoring System (MEMS) cap to record the number of bottle openings and date/time of each opening. Riboflavin will be added to medication capsules and urine ultraviolet fluorescent tests will be conducted at weekly clinic visits to assess compliance. Participants will receive \$10 at each clinic visit in which results from self-report, MEMS, and riboflavin are all consistent with medication compliance.

Human Laboratory Procedures (Specific Aim 1). On Study Weeks 0 and 4, participants will engage in the cold-pressor task (CPT). The CPT is widely used as a stress-inducer in human laboratory studies and elicits moderate activation of the sympathetic nervous system and limited activation of the HPA-axis, which are two major stress systems in the body⁷⁵⁻⁷⁸. HPA-axis activation during the CPT can be increased by incorporating a social evaluative component. Specifically, a study member of the opposite sex of the study participant will dress in a white labcoat and be physically present during the CPT. Additionally, participants will be videotaped and informed that their facial expressions will be assessed during the CPT. The addition of the social component during the CPT has been demonstrated to selectively activate the HPA-axis and significantly increase salivary cortisol levels⁷⁷. During the CPT, participants will submerge their dominant arm in an ice-water bath for up to 2 minutes. Stress levels will be assessed using subjective and physiological measures HR, BP, and salivary cortisol consistent with previous studies from our group^{79,80}. Alcohol craving will be assessed using a 4-item questionnaire⁵⁷.

Table 2. Time Course for Assessing Stress-Induced Relapse Risk

Time (pm)	Study Procedures
3:00	Assess Craving, BAAD, Stress, Cortisol, HR, BP
3:15	Cold Pressor Task
3:20	Assess Craving, BAAD, Stress, HR, BP
3:45	Assess Craving, BAAD, Stress, Cortisol, HR, BP

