Natural Environment Procedures (Specific Aim 2). At Study Week 0, all participants will receive a pamphlet copy of the “Rethinking Drinking: Alcohol and Your Health” providing research-based information related to alcohol use (RethinkingDrinking.niaaa.nih.gov). Research staff will go over the pamphlet’s information with the participant at the initial visit and subsequent visits as necessary. At each study visit, participants will receive study medication for the week and assessed for adverse events and medication compliance. At each visit, participants will also be assessed for recent alcohol use (self-report, ETG, BrAC), alcohol craving (PACS), and stress/anxiety (HAM-A, PSS). At the end of the study, participants will be referred to local alcohol treatment services as needed.

Participant Payment & Compensation. Participants will receive be able to receive \$300 for completing the study (\$50 for completing baseline screening; \$25 for each visit (\$100); \$25 for stress reactivity assessments (\$50); and \$100 completion bonus). Additionally, participants will potentially receive \$10/week (up to \$40) for demonstrating medication compliance. Participants will also receive parking/bus fare compensation at each visit worth \$5.

DATA ANALYSIS PLAN

General Data Analytic Strategy. Analyses will proceed in parallel using frequentist and Bayesian statistical inference. Frequentist analyses will examine relationships between predictors and outcomes using traditional measures of effect size and statistical significance (i.e., regression coefficients, standard errors,

confidence intervals, and p -values), while Bayesian analyses will measure uncertainty in model parameter estimates via posterior distributions and directly evaluate the probability of the alternative hypothesis.

Specific Aim 1: assess pre- to post-treatment reductions in stress reactivity (self-report, salivary cortisol, heart rate, blood pressure) and stress-induced alcohol craving (self-report, alcohol demand) in the human laboratory setting.

Hypothesis 1: We will observe pre- to post- treatment reductions in stress reactivity and stress-induced alcohol craving. Generalized linear mixed modeling will be used to evaluate each outcome as a function of time (pre-test and post-test) in unique models.

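### Entry requires a craving rise in the Week 0 stress session, which is also the only Aim 1 pre-treatment value, so selection alone may produce part of any fall in the self-report craving rise by Week 4

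*Combined protocol and SAP*

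**What the plan says.** Under Participants, Recruitment, and Setting, the inclusion criteria end with "or moderate stress (score 14 to 26), respectively; and increase in alcohol craving following the", and the sentence finishes "baseline stress reactivity assessment. Individuals will be excluded for exhibiting severe scores". No minimum rise and no time point are given.

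Human Laboratory Procedures (Specific Aim 1) states "On Study Weeks 0 and 4, participants will engage in the cold-pressor task (CPT"). Table 1 marks the same two weeks, and Participant Payment & Compensation pays for two stress sessions ($25 each, $50 in all). No separate screening session is described.

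Table 2 measures craving once before the cold pressor (3:00) and twice after it (3:20 and 3:45). The 3:20 row reads "Assess Craving, BAAD, Stress, HR, BP", so craving is listed apart from alcohol demand (the BAAD). The craving instrument differs between sections that cite the same reference: "will be assessed using a 5-item questionnaire" under Alcohol-Related Measures, and "Alcohol craving will be assessed using a 4-item questionnaire" under Human Laboratory Procedures.

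The Data Analysis Plan for Aim 1 covers "stress-induced alcohol craving (self-report, alcohol demand) in the human laboratory setting", and the model is: "Generalized linear mixed modeling will be used to evaluate each outcome as a function of time (pre-test and post-test) in unique models". It has no arm term, although Overall study design and Table 1 say that participants get either pioglitazone or placebo. The plan does not discuss regression to the mean.

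**The concern.** People enter because their craving rose at Week 0. Week 4 carries no such condition. Where a candidate's Week 0 rise is partly a matter of the day, those who pass include some whose rise was unusually high that day, and they will tend to show a smaller rise next time. Hypothesis 1 predicts a reduction, so the artefact looks like success, and a model with time as its only predictor cannot separate the two. A Bayesian analysis of the same time effect has the same problem.

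Self-report is one of two stress-induced craving measures in Aim 1; alcohol demand is the other. Power/Sample Size Considerations expects the posteriors to inform effect sizes or priors for later research. An inflated estimate could therefore outlast this pilot.

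**Working it through.** **Plan's own figure.** There is none for craving. The only power statement (80%, N = 20, one-tailed 0.05, a 20% decrease) concerns drinking and does not bear on this point.

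**Which session selects.** That the baseline assessment is the Week 0 session is an inference. Table 1, the laboratory section and the two-session payment all support it.

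**Direction.** Let D0 and D4 be the rise (post-stress minus pre-stress craving) at Weeks 0 and 4, with the same distribution at both weeks and no drug effect. Entry keeps the share p with the highest D0. The mean of D4 in those people cannot exceed the mean of the top share p of D4. So selection cannot create an expected increase. It creates a fall unless the same people would pass on a repeat test.

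**Illustrative size.** N = 20 is from the plan. The rest is assumed, because the documents give no mean, SD, retest correlation or screen-fail share. Take D0 and D4 as bivariate normal with mean m and SD 1, retest correlation r, and entry if D0 > 0. Then:

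- share passing: p = Phi(m)
- mean at Week 0 among those entered: m + phi(m)/Phi(m)
- mean at Week 4: m + r × phi(m)/Phi(m)
- expected fall: (1 − r) × phi(m)/Phi(m)

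For m = 0.5, phi/Phi = 0.352/0.691 = 0.509. With r = 0.5 the rise goes from 1.01 to 0.75 SD, a fall of 0.5 × 0.509 = 0.25 SD, or 25%. For m = 1 and r = 0.7 the fall is 0.3 × 0.288 = 0.086 SD. Without the entry criterion it is 0.

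Simulated chance of declaring a reduction with no drug effect (n = 20, paired t as a stand-in for the mixed model; repeat runs agree to within about one percentage point):

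| Share passing | One-sided 0.05, r = 0.7 / 0.5 / 0.3 | Two-sided 0.05, reductions only (nominal 2.5%), r = 0.7 / 0.5 / 0.3 |
|---|---|---|
| 98% (m = 2) | 6 / 6 / 7% | 3 / 3 / 3% |
| 84% (m = 1) | 12 / 16 / 19% | 7 / 9 / 11% |
| 69% (m = 0.5) | 22 / 32 / 41% | 14 / 21 / 29% |

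The plan states the one-sided level only for the drinking calculation.

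**When the fall is nil.** Suppose 31% never respond (rise of zero at both sessions) and 69% always rise by a positive amount that varies independently between sessions, with an assumed coefficient of variation of 0.5. Then r = 0.31/(0.31 + 0.25) = 0.55 and 69% pass. Yet the expected rise among those entered is the same at both weeks, so the fall is 0. The normal formula at 69% passing and r = 0.55 would have given 0.45 × 0.509 = 0.23 SD. The result depends on the distribution as well as on r.

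**Other outcomes (normal model, one-sided).** Taking the cells 84% passing with r = 0.7, and 69% passing with r = 0.5: post-stress level 6–9% and 8–20%, depending on how resting craving relates to the rise; an outcome correlated 0.3 with the self-report rise 7% and 9%; correlated 0.5, 8% and 14%; uncorrelated, 5%.

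**Remedy check.** Comparing arms at Week 4 with the Week 0 response as covariate gives 4.9–5.0% false positives one-sided, since both arms are selected alike. With an assumed 10 per arm, the normal approximation to the difference detectable with 80% power is (1.645 + 0.842) × √(2/10) × √(1 − r²) = 1.11 × √(1 − r²), or 0.79, 0.96 and 1.06 SD for r = 0.7, 0.5 and 0.3. Simulation with the t distribution gives 0.85, 1.04 and 1.14 SD.

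**The case against.** The strongest objection is to generality. A reader might infer that a fall is certain whenever some candidates fail and the retest correlation is below 1. The documents do not support that: the stable non-responder example meets both conditions and gives no fall, and nothing in the plan says whether non-response is a trait or noise. This objection stands, and the conclusion is conditional because of it.

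The outcome definition is also open. Aim 1 does not say whether the craving outcome is a rise, a post-stress level or an average of readings. Reading the criterion as self-report is itself an inference, because Aim 1 counts alcohol demand as a craving measure too; the separate listing in Table 2 favours self-report. A level or average would be affected less. Any increase qualifies for entry, so most candidates may pass, and with 98% passing the distortion is negligible.

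Finally, enriching for people whose craving responds to stress is a legitimate choice in a self-described preliminary study, and any uncontrolled pre-post change is weak evidence anyway. Both are true. But this contributor comes from the plan's own entry rule, points in the hypothesised direction, and affects an estimate that may be carried forward. The mention of placebo does not answer it, because the Aim 1 model does not use an arm.

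**Conclusion.** The concern holds conditionally and should be addressed. The selecting session doubles as the only pre-treatment value, and the analysis has no comparator. If the outcome is the self-report rise and passing is partly within-person variation, a fall is expected with no drug effect. It is nil if non-response is perfectly stable or nobody fails.

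The size is unknown. The tabulated one-sided rates, about 6% to 41% against a nominal 5%, illustrate one assumed model and do not estimate this trial's error rate. A reader might also infer that all of Aim 1 is biased. The documents do not support that: alcohol demand, self-reported stress, cortisol, heart rate and blood pressure are affected only as far as they correlate with the craving rise. Confidence is medium: the structural facts are clear, but the outcome definition and the magnitude are not.

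**What to change.** 1. Reconcile the mention of placebo (Overall study design, Table 1) with the time-only analysis.
2. If there is a randomised placebo group, test self-report stress-induced craving as pioglitazone versus placebo at Week 4 with the Week 0 response as covariate. This is a change to the analysis text. Its price is precision: with an assumed 10 per arm, 80% power is reached only for differences of about 0.85–1.14 SD one-sided.
3. If the study is single-arm, do not interpret the raw pre-post change in self-report craving as a drug effect, or use it for future effect sizes or priors, without stating that selection on the Week 0 response may contribute. Any regression-to-the-mean range should be a sensitivity analysis only. It should state that it depends on the assumed retest correlation and the assumed normal distribution, and it needs the scores of candidates who fail the criterion, which the documents do not say are kept. Even under the normal model, overstating r by 0.2 leaves 10–15% false reductions, and understating it by 0.2 gives about 2%. If non-response is a stable trait, the correction would remove a bias that is not there.
4. As supporting wording, name the craving score and post-stress time point (3:20 or 3:45) used for eligibility and for the outcome, and reconcile the 5-item and 4-item questionnaires.

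Apart from keeping the screen-failure scores, these are wording and analysis-plan changes.

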The primary purpose of the current proposal is to obtain preliminary data to increase the likelihood of funding for a future NIH grant, while balancing the feasibility of completing the current proposal. To that end, we will utilize a within-subject, repeated measures design to assess the feasibility of administering pioglitazone for four weeks to non-treatment and treatment-seeking individuals with AUD and elevated levels of stress/anxiety (**N=20**). Participants will undergo pre- and post-treatment human laboratory assessment of stress-reactivity and stress-induced alcohol craving. During treatment, changes in alcohol use, stress/anxiety, and alcohol craving will be assessed in the natural environment. The study design features 1) rigorous monitoring of medication compliance (Medication Event Monitoring System (MEMs)) and alcohol use (urinary ethyl glucuronide (ETG)); 2) biological assessment of stress reactivity (salivary cortisol, blood pressure, and heart rate); and 3) a multi-dimensional assessment of stress-induced alcohol craving incorporating both traditional measures of alcohol craving in addition to relatively novel behavioral economic measures (delay discounting, alcohol demand). Taking these measures together, we hope to present a robust and comprehensive characterization of pioglitazone on alcohol use, stress reactivity, and stress-induced alcohol craving.

SPECIFIC AIMS

Specific Aim 1: To assess pre- to post-treatment reductions in stress reactivity (self-report, salivary cortisol, heart rate, blood pressure) and stress-induced alcohol craving (self-report, alcohol demand) in the human laboratory setting.

Hypothesis 1: *We will observe pre- to post- treatment reductions in stress reactivity and stress-induced alcohol craving.*

Specific Aim 2: To assess changes in alcohol drinking (drinks per day, heavy drinking days), stress/anxiety (PSS, HAMA, PCL-5), and alcohol craving (PACS, delay discounting, alcohol demand) during treatment in the natural environmental setting.

Hypothesis 2: *We will observe decreased alcohol drinking, stress/anxiety, and alcohol craving over the course of treatment.*

There is increasing attention and evidence supporting the potential role of the PPAR γ system as a novel target in the treatment of AUD. From a translational perspective, this study is timely and likely to advance our understanding of stress as a mechanism of action of pioglitazone effects.

IRB NUMBER: HSC-MS-18-0922

BACKGROUND AND RATIONALE

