and predict alcohol treatment response³⁹⁻⁴². Delay discounting and alcohol demand are poorly correlated with each other, supporting a multi-dimensional model in which these measures represent distinct aspects of motivation to use alcohol⁴²⁻⁴⁸. In the current proposal, we will assess changes in both delay discounting and alcohol demand over Study Weeks 0 to 4 and alcohol demand will be used to assess state-dependent changes during the human laboratory stress-reactivity assessment.

METHODS

Research team. The research team will consist of [name] (PI) and a number of collaborators from UTHealth and Brown University. [name] (PI) is an experienced addiction researcher and an expert in assessing behavioral economic measures in addiction research, which is pertinent to the current project. Drs. [name] (CNRA Medical Director) and [name] (Addictions Psychiatrist) will provide medical guidance and ensure participant safety over the course of the study. [name] is Professor and Vice Chair for Research and directs the Behavioral Laboratory at the CNRA with expertise in medication development trials as well as alcohol studies. [name] is a biostatistician and data scientist with expertise in experimental design and statistical modeling, including the type of generalized linear modeling that will be utilized by the present research. From Brown University, [name] (Co-I) is serving as a consultant on this project and is an expert in stress and alcohol research¹⁻⁷. Additionally, our group has a history of collaborating with the Laboratory of Biomarkers located in the BBSB for analyzing biological samples, such as salivary cortisol in the current protocol. We will work with [name] to ensure that samples are collected and analyzed appropriately.

Overall study design. We will utilize a within-subject, repeated measures design. Participants will receive pioglitazone or placebo for four weeks. A summary of the study timeline, procedures, and assessments is shown in the following Table.

Table 1. Outline of Study Timeline, Procedures, and Assessments

Study Week Procedures and Assessments	0	1	2	3	4
Consent and Baseline Screening SCID, ASI, KMSK, TLFB, CIWAA, AUDIT	X				
Receive Study Medication (Pioglitazone or Placebo) Assess Medication Compliance and Adverse Events	X	X	X	X	X
Human Laboratory Procedures (Specific Aim 1) Stress-Reactivity Assessment (Salivary Cortisol, HR, BP, Craving) Alcohol Demand, Alcohol Ladder	X				X

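### The Aim 1 model contains only time, so it cannot separate an effect of pioglitazone from the effect of meeting the same cold-pressor stressor a second time

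*Combined protocol and SAP*

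**What the plan says.** The Human Laboratory Procedures section schedules the stressor twice: "On Study Weeks 0 and 4, participants will engage in the cold-pressor task (CPT"). A single description covers both sessions. In it, "participants will submerge their dominant arm in an ice-water bath for up to 2 minutes", with an opposite-sex observer in a white coat, and "participants will be videotaped and informed that their facial expressions will be assessed during the CPT". The section relies on this social element to strengthen activation of the HPA axis. Table 2 sets readings at 3:00 (before the task), 3:20 and 3:45, with cortisol at 3:00 and 3:45 only.

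Hypothesis 1 reads: "We will observe pre- to post- treatment reductions in stress reactivity and stress-induced alcohol craving". Its analysis is: "Generalized linear mixed modeling will be used to evaluate each outcome as a function of time (pre-test and post-test) in unique models". No treatment term is named.

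On design, the Overall study design paragraph says "We will utilize a within-subject, repeated measures design" and then "Participants will receive pioglitazone or placebo for four weeks"; Table 1 also lists placebo. No randomisation, allocation ratio, blinding or between-arm comparison is described.

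On interpretation, the Abstract hopes for "a robust and comprehensive characterization of pioglitazone on alcohol use, stress reactivity, and stress-induced alcohol craving". The Power/Sample Size paragraph would use the posterior of each effect to inform effect sizes and priors in later work.

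**The concern.** Week 0 comes before treatment, because a craving rise at the baseline stress assessment is an entry criterion. It is also everyone's first session. Week 4 follows four weeks of study medication and is everyone's second session with the same task. In a model with time as its only predictor, after treatment and second exposure are one variable.

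If people respond less to a stressor they have already met, the pre-to-post coefficient shows a reduction even when the drug is inert. The document mentions neither habituation nor anticipation. It describes no familiarisation session, non-stress control session or counterbalancing.

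What is at stake is the Aim 1 conclusion and its later use. A repeat-session effect recorded as a drug effect would inflate the effect size, or shift the prior, from which the next trial is planned.

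**Working it through.** **The plan's own figure.** There is none to reproduce here. The only power statement (80% for a 20% fall in drinking) concerns Aim 2. No SD, correlation or effect size is given for any stress-reactivity outcome.

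**What the coefficient estimates.** Let δ be the mean drug effect on the response, η the mean effect of being in the second session, and π the proportion on active drug. The expected Week 4 minus Week 0 change is πδ + η, or δ + η if everyone takes pioglitazone. With time as the only predictor, one number is estimated for two unknowns. More participants sharpen the sum but do not split it. The Bayesian posterior describes the same sum.

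**Direction.** Habituation lowers the second response, which favours Hypothesis 1. For anticipation, suppose it adds *a* to the Week 4 reading at 3:00.
- If later readings are unchanged, a rise score (later minus 3:00) falls by *a*, which favours Hypothesis 1.
- If reactivity is scored as a level that includes the 3:00 reading, the Week 4 value goes up, which works against it.
- If later readings also rise by *a*, the rise score is unchanged and the level goes up.

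The plan does not define reactivity as a rise, a peak or a level, so the sign is open.

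**Size, under assumptions.** With two complete sessions and a Gaussian outcome, the time-only mixed model reduces to a paired t test.

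- From the document: N = 20, hence 19 df. One-sided 0.05 is stated only for the drinking power calculation, so two-sided 0.05 is shown too.
- Assumed: no drug effect; second response smaller by a fraction h; coefficient of variation (CV) of the response between persons 0.75 to 1.0; test-retest correlation r of 0.5 to 0.7; equal SD in both sessions.
- Formula: dz = h / (CV × √(2(1 − r))). The rejection probability comes from the noncentral t with noncentrality dz × √20 and critical value 1.729 (one-sided) or 2.093 (two-sided).

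The denominator runs from 0.75 × √0.6 = 0.581 to 1.0 × √1.0 = 1.0.

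| h | dz | False reduction, one-sided 5% | Two-sided 5%, reductions only |
|---|---|---|---|
| 0 | 0 | 5% | 2.5% |
| 10% | 0.10–0.17 | 11–18% | 6–11% |
| 20% | 0.20–0.34 | 22–44% | 13–31% |
| 30% | 0.30–0.52 | 36–72% | 25–59% |

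Outside that range, h = 20% with CV 1.25 and r = 0.3 gives dz = 0.2/(1.25 × √1.4) = 0.135 and 14% one-sided.

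**Bayesian analysis.** With a flat prior and known SD, the typical posterior probability of a reduction is Φ(dz × √20): 0.81 at dz = 0.2, 0.91 at 0.3 and 0.987 at 0.5, all with an inert drug.

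**With a placebo contrast.** Assume 10 per arm and a repeat-session effect common to both. A two-sample test on the change scores then keeps its type I error at 4.8–5.1% in simulation, for repeat-session effects from 0 to 0.8 SD of change. Power at one-sided 5% is 28.5%, 53% and 69% for between-arm differences of 0.5, 0.8 and 1.0 SD of change. Reaching 80% needs 51, 21 and 14 per arm.

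**The case against.** The strongest reply is that the document mentions placebo. If some participants take it, Week 4 is not always on drug, and the placebo participants carry the same repeat-session effect. A reader might infer from the schedule that session order is wholly tied to treatment. With the placebo wording unreconciled, the documents do not establish that. What remains is narrower: the written model has no treatment term, so it would pool any placebo participants under time and still could not isolate the drug.

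Second, a reader might take habituation as certain, because the task leans on social evaluation. The document says only that the social element activates the HPA axis and raises cortisol; it says nothing about repetition after four weeks. It also says the cold pressor itself moderately activates the sympathetic system, so a weaker social element need not carry over to heart rate or blood pressure. Nor does it say whether the Week 4 observer is someone the participant has met. This stands: a repeat-session effect is possible, not shown.

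Third, this is a 20-person pilot for preliminary data, and Hypothesis 1 predicts only an observed change. That lowers the need for confirmatory control. It does not cover reading the change as a pioglitazone effect or carrying it forward as an effect size or prior.

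**Conclusion.** The concern holds in this form: as written, the Hypothesis 1 coefficient is drug effect plus repeat-session effect, and the planned analysis cannot separate them. That follows from the schedule and the model and needs no assumed number.

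How much it matters does rest on assumptions. Under those stated, the chance of a false reduction rises from a nominal one-sided 5% to 11–18%, 22–44% or 36–72% for a second response 10%, 20% or 30% smaller. These figures show what could happen, per outcome; they do not estimate how likely it is.

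A reader might also infer that the bias favours Hypothesis 1 on every Aim 1 outcome. The documents do not support that: habituation would act that way, but the direction of anticipation depends on how reactivity is scored.

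**What to change.** 1. Reconcile the statement that participants receive pioglitazone or placebo (Overall study design, Table 1) with the single-group, time-only analysis. If a concurrent placebo group exists, state how participants are allocated and make treatment-by-time the Aim 1 contrast. This removes a repeat-session effect common to both arms. The cost is power, as shown above for 10 per arm.
2. If there is no placebo group, restate Hypothesis 1 and the Aim 1 conclusion as the change from a first to a second stress session over four weeks of treatment. Say that this is not by itself evidence of a drug effect, and do not carry it forward as a drug effect size or prior.
3. In either case, report the 3:00 pre-stressor values by session beside the response, so that a smaller rise caused by a higher Week 4 starting value is not read as reduced reactivity. Table 2 already collects them.

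Using a different observer at Week 4 is not recommended: it would tie observer identity to session and leave familiarity with the cold task untouched.

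Items 2 and 3 need only wording and reporting. The downside is a weaker permitted conclusion for Aim 1.
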